7.2 Participant Tracking

Each recruited participant will be tracked closely throughout study enrollment. If desired, a study events calendar will be created for each participant. Any outstanding or incomplete visits will be accessible in real time to the project director and study team. The study team will maintain regular communications with each study participant throughout enrollment, through regularly scheduled follow up calls, and established retention strategies will be used as discussed in §4.6.

CHAPTER 8 DATA SAFETY MONITORING PLAN

8.1 Participant Risks

Participation in this ancillary study may be associated with minor risks or safety concerns. The potential risks of this study fall into 5 categories: 1) those related to research participation; 2) those related to testing procedures; 3) those related to the intervention or control products; and 4) those related to depressive symptoms. The risks are outlined for each category below:

Minor Risk of Participation in Research: With any study, risk of breach of confidentiality is possible since we are collecting personal health information.

Minor Risk of Testing Procedures: The potential risks of the testing procedures are minor since the majority will be questionnaire based assessments. It is possible that participants may find the questionnaires tedious or may be uncomfortable being asked about sensitive topics like suicidality. It may also be unpleasant to collect a fecal sample.

Minor Risk Related to Intervention or Control Products: We do not anticipate any major risks for the participants with consumption of either the intervention (freeze dried blueberry powder) or control (placebo powder) products. Participants might grow weary and uninterested in consuming the products each day over the 12-week period. Additionally, the proposed intervention will provide an older adult with 30% of the recommended daily intake of dietary fiber. One may experience side effects that commonly occur with increased dietary fiber consumption if the individual typically consumes relatively low amounts of dietary fiber.

Risk Related to Depressive Symptoms: It is possible that individuals with depressive symptoms may progress in symptom severity during the study period. Although we do not anticipate a change to a more severe category of depression, we recognize that our proposed population of older adults with prevalent depressive symptoms are already predisposed to development of more severe depressive disorders. Importantly, our population of interest is also more likely to experience suicidal ideation.

8.2 Risk Minimization

We will attempt to minimize the identified risks as specified below:

Risk Minimization of Participation in Research: To minimize the risk of breach in confidentiality, all primary study data will be recorded with computer tablets on electronic case report forms (CRF) or as digital files generated from laboratory equipment. All data recording will be in accordance with procedures and guidelines outlined in the study's Manual of Procedures (MOP) authored by the study team. Participant confidentiality will be maintained by recording subject data using a unique subject identifier. Identifiable data, such as contact information and medical record numbers, will be recorded and stored separately from the clinical study data. Any paper-based study material and any identifiable data will be kept separate in a locked file cabinet accessible by authorized study staff only. Only the

study staff directly responsible for the data collection and the safety of the participant will have access to identifiable information. All electronic CRF data will be stored securely in an electronic data capture and management system. Raw electronic instrumentation data will be organized and saved on a private network file dedicated to the research project. Only those listed on the approved IRB protocol will have access to subject data. Subject data will be coded and locked in a file cabinet in a locked office. Identifying information will not be used during discussion, presentation or research publication. All documents and electronic data will be archived for a minimum of three years, or as required by the IRB and federal regulations, after the completion of the clinical trial. The study will be registered at clinicaltrials.gov.

The Hinda and Arthur Marcus Institute for Aging Research employs the Research Electronic Data Capture (REDCap) system for data capture and data management operations. REDCap is a full-featured clinical trials data management system (DMS) accessible to data entry and data analysis workstations using secure Web technologies. While REDCap can be used to collect virtually any type of data (including 21 CFR Part 11, FISMA, and HIPAA-compliant environments), it is specifically geared to support online or offline data capture for research studies and operations. REDCap is developed and maintained by Vanderbilt University in cooperation with REDCap Consortium members, including HRC. HSL hosts and maintains a dedicated instance of REDCap for use across our research enterprise. Each research project is provided separate workspace in which all of the study data are stored in a MySQL relational database on the private corporate network behind several firewalls and located physically within the HSL data center.

Risk Minimization of Testing Procedures: The majority of the testing procedures will be questionnaire based. Participants will be advised that they can refuse to answer any of the questions. Participants will be permitted to rest between studies to prevent fatigue. To minimize the risk of being uncomfortable during questionnaires on sensitive topics like suicidality, only trained research staff will administer the questionnaires. Research staff will be trained to administer them in a calm, welcoming demeanor and will reassure the participants that the assessment(s) can stop at any time.

To avoid any unpleasant experience collected a fecal sample, study staff will provide detailed instruction on how to collect the sample. Furthermore, to avoid the burden of storing it in the participants freezer, study staff will pick up the collected sample as soon as possible from the study participant.

Risk Minimization of Intervention Product: Individuals with allergies to intervention products will not be included in this study to avoid any adverse effects/allergic reactions. We anticipate that the blueberry and placebo powder will be well-tolerated by participants since they consist of dietary nutrients that are regularly consumed. Regardless, every 4 weeks we will ask participants about any complaints or adverse events that are directly related to the study intervention products. We plan to track diarrhea, gas, bloating, abdominal pain, constipation etc. Since the intervention arm will be increasing fiber consumption and sudden changes in fiber intake may cause gastrointestinal distress, participants will be counseled to consume their dietary intervention products alone (i.e. without other foods) to avoid consumption of large quantities of fiber at one time. Since our intervention provides only ~30% of the recommended intake of daily fiber, we do not anticipate this amount will result gastrointestinal distress, if consumed alone. Nevertheless, symptoms of gastrointestinal distress will be captured at each visit and appropriately addressed by the study team. [name], who has a PhD in Nutrition, will consult with participants on their experience with the fiber and reconcile any gastrointestinal stress. If a participant develops a health problem or a potential health problem (in addition to the ones outlined below), the PI will be notified ASAP. If necessary, the SO will be contacted to help decide whether the participant should continue in the study, and/or what further steps regarding medical evaluation should be performed.

Risk Minimization of Depression Severity: Although we do not anticipate a change to a more severe form of depression, we recognize that our proposed population of older adults with prevalent

depressive symptoms are already predisposed to development of more severe depressive disorders. The level of depression will be evaluated and monitored at all visits (except for the telephone screen) to proactively monitor participant safety. If at any time during the study an individual's assessments indicate they have progressed to a more severe forms of depression, then specific safety protocols will be followed (e.g., notifying the study psychiatrist and/or PI). Our population of interested is also more likely to experience suicidal ideation, which will also be monitored at every visit to identify any individuals, who may need psychiatric care outside this study. If the participant is deemed to be dangerous or at imminent risk of harm, study staff will contact emergency services (i.e., #911) for immediate medical assistance.

General Risk Minimization: The proposed protocol requires 5 visits over a total 14 weeks and therefore imposes a moderate amount of participant burden with respect to time and effort. Our institute has a strong track record of successful clinical research requiring similar participation, and retention has been high in these projects. The Clinical Research Laboratory at the Marcus Institute is located near a cafeteria and rest room, and is equipped with comfortable seating, a TV, movies, books, and magazines to keep individuals occupied during rest periods. Several additional strategies will be employed to minimize participant burden and maximize adherence to the protocol. We will:

- Develop a personal relationship between participants and members of the staff.
- Schedule appointments at convenient times with familiar staff.
- Explain to participants all aspects of their participation and follow up. We will demonstrate and practice study procedures before beginning data collection.
- Provide reminders of all appointments and follow-up phone calls.
- Include personal notes in the participant's data file to remember events in the life of the participant; these can be commented on at the next visit (e.g., birthday, birth of a grandchild).
- Provide snacks and lunch during all visits.
- Provide transportation for all visits, if required.
- Provide valet or dedicated on-site parking spaces.
- Compensate participants for visits.

8.3 Quality Assurance and Safety Monitoring

The Principal Investigator (PI) will assume primary responsible for ensuring participants' safety on a daily basis. Since this is a single-site, phase 1 pilot study, without high risk, our study will not require an official Data and Safety Monitoring Board (DSMB). However, to ensure and monitor participant safety, any adverse event will be documented. The PI will have the support of her co-investigators, Drs. [name] and [name], who are both geriatricians and will assist the PI assessing severity and relatedness of any safety events.

8.4 Adverse Event Collection and Reporting

Any adverse or serious adverse events will be logged using forms either provided by or modeled after the forms that are provided by the NIA Clinical Research Toolbox. Since there is no separate screening visit for this specific study, the baseline visit will mark the beginning of when any potential adverse or serious adverse events could occur/be collected. All other AE's will be collected as a part of the parent study.

Adverse Event Definition and Categorization

An adverse event is any untoward medical occurrence in a participant, whether or not it is causally related to the study. An adverse event can therefore be any unfavorable and unintended sign (including an abnormal laboratory finding, for example), symptom or disease temporally associated with the study. Adverse events will be recorded on the appropriate case report forms and source documents. The PI and/or trained staff member will evaluate all adverse events as to their severity and relation to the study. The severity of adverse events will be graded as follows:

Mild: Awareness of a sign or symptom but easily tolerated.

Moderate: Discomfort sufficient to cause interference with usual activity or to affect clinical status.

Severe: Incapacitating with inability to do usual activity or to significantly affect clinical status.

Life Threatening: The participant was at immediate risk of death from the adverse event as it occurred.

The Investigator will also assess the relationship of any adverse event to the study, based upon available information, using the following guidelines:

- 0 = Unlikely: No temporal association, or the cause of the event has been identified
- 1 = Possible: Temporal association, but other etiologies are likely to be the cause; however, involvement of the study procedures cannot be excluded.
- 2 = Probable: Temporal association, other etiologies are possible, but not likely.

To determine the attribution and temporal association of an adverse event we will consider the following:

- 1) Whether the participant reports they have experienced the same symptom prior to the study intervention.
- 2) Whether the symptom occurred and resolved within 24 hours of taking the study intervention.

The PI and study staff will consider the symptom according to the conditions stated above and determine temporality as per clinical judgment.

Definition of a Serious Adverse Event

A serious adverse event is any experience that results in any of the following outcomes:

- Death
- Is life-threatening
- Inpatient hospitalization or prolongation of hospitalization

A persistent or significant disability/incapacity. Important medical events that may not result in death, be life-threatening, or require hospitalization may be considered a serious adverse event when, based upon appropriate medical judgment, they may jeopardize the patient or participant and may require medical or surgical intervention to prevent one of the outcomes listed in this definition. We do not anticipate any Serious Adverse Events with our intervention.

Adverse and Serious Adverse Event Reporting

There is a potential for adverse events and incidental findings during this study. A structured questionnaire asking about adverse events will be assessed during each visit of the intervention period. However, when any adverse has been identified, the study team will take appropriate action necessary to protect the study subject and then complete the Adverse Event form that will be modeled after the form provided by the NIA Clinical Research Toolbox. This form requires Principal Investigator review and signature. After review by the Principal Investigator any adverse event will be reported to the IRB as appropriate.

AE's that 1) are unexpected in nature, severity, or frequency, 2) are possibly, probably, or definitely related, and 3) suggests that the research places participants at a greater risk of harm than previously known or recognized, will be reported to the IRB as appropriate (e.g., within 2 weeks of the event).

If a serious event occurs, it will be brought immediately to the attention of the Principal Investigator, who will discuss the event with the co-investigators and together decide if immediate treatment is necessary. If such treatment is necessary, the PI, co-investigators, or the study staff will coordinate such treatment at an appropriate hospital or urgent care setting, contact the primary care physician, and notify the IRB. A Serious Adverse Event form that is modeled after the one provided by the NIA Clinical Research Toolbox will be completed, which requires Principal Investigator review and signature. If an AE is defined as a SAE, the Principal Investigator will be notified as soon as the event is known about. Routine reporting of any SAEs will be reported to the IRB within as appropriate.

Unanticipated problems or adverse events will be reported according to Advarra's IRB written guidelines for interventional studies. Unanticipated problems and serious adverse events that are probably, possibly, or definitely related to the study will be reported as soon as possible from the time of learning of the event, but reported within 10 days to Advarra's IRB per Advarra IRB guidelines. Advarra will be provided a written report submitted and a submission of the incident via the eIRB system. This form will record any adverse symptoms and/or study protocol deviations. Study staff will reference a Subject Safety Event Reporting Decision Chart

provided and updated regularly by Advarra to determine whether an event needs to be reported to the Advarra IRB.

All other adverse events/study incidents will be logged on an Adverse Event log and reported to the IRB following the appropriate reporting times as defined by the Advarra IRB.

For less serious or incidental findings the Principal Investigator will speak with the participant about the finding. If necessary, the PI may suggest appropriate follow-up with their clinical provider and/or provide a letter describing the findings and need for follow-up.

Any adverse events that take place during testing will be reported to the PI and recorded in the database. The PI will have ultimate responsibility for monitoring participant safety in the trial. The investigators will be responsible for reviewing each adverse event in a timely fashion, and reporting all incidents to the appropriate regulatory agencies according to written guidelines.

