5.3 Dietary Intervention

The duration of this study will be a total of 14 weeks. The first two weeks will require participants to avoid eating fiber- and anthocyanin-rich foods.

Individuals will then be randomized to either the intervention or the control group. This is a double-blinded study, so the study staff not the participant will know what powder the participants are assigned to. Those randomized to the intervention group will be asked to consume approximately 48 g of freeze-dried blueberry powder as a source of ~8 g of fiber and 600 mg of anthocyanins. The proposed dose of 48 g of freeze-dried blueberry powder is equivalent to approximately 2 cups of whole blueberries. Individuals randomized to the control group will be asked to consume approximately 48 g of a nutritionally matched placebo powder that is devoid of anthocyanins and fiber.

The powders will be individually packaged in 24 g amounts. Participants will be instructed to consume their respective powder, mixed in an 8 fl oz glass of water twice per day for 12 weeks. They will be asked to consume 24 g in the morning and 24 g in the afternoon. Given that intervention and control products are regularly consumed, we do not anticipate any toxicities.

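### Section 8.4 asks whether a symptom both began and cleared within 24 hours of a dose; with twice-daily dosing only the clearing half discriminates, and it leans against persistent product effects

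*Combined protocol and SAP*

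**What the plan says.** Section 8.4 of the combined protocol and SAP grades relatedness as Unlikely, Possible or Probable. The two higher grades each presuppose a temporal association. The lowest is defined as "0 = Unlikely: No temporal association, or the cause of the event has been identified".

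To settle attribution and temporal association, the section names two things to consider. The first is whether the participant had the same symptom before the intervention. The second is "Whether the symptom occurred and resolved within 24 hours of taking the study intervention". It then adds: "The PI and study staff will consider the symptom according to the conditions stated above and determine temporality as per clinical judgment". On who grades, it says "The PI and/or trained staff member will evaluate all adverse events as to their severity and relation to the study", and the sentence introducing the scale gives the assessment to the Investigator, using whatever information is to hand.

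On dosing, section 5.3 sets two 24 g packets a day for 12 weeks: "They will be asked to consume 24 g in the morning and 24 g in the afternoon". On expected effects, section 8.2 says "We plan to track diarrhea, gas, bloating, abdominal pain, constipation etc".

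Relatedness is then used later in section 8.4. One IRB route covers events that are unexpected, that "are possibly, probably, or definitely related", and that suggest a greater risk than was known. Another sets a 10-day limit for related serious adverse events and unanticipated problems.

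**The concern.** A temporal prompt should help to separate events the powder caused from events it did not. This one joins two conditions. Under continuous twice-daily dosing the first (onset within 24 hours of a dose) is met by almost everything, whatever the cause. The second (resolution within the same window) then does the sorting, and it sorts by duration.

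That suits gas that follows a dose and settles. It does not suit an effect of sustained exposure. Section 8.2 itself warns that a sudden rise in fiber can cause gut distress, and participants start about 8 g a day after two weeks of avoiding fiber-rich foods. Constipation or abdominal pain that continues while the powder continues would draw a *no*. Because absence of temporal association is the definition of the lowest grade, a *no* leans towards Unlikely.

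At stake is the accuracy of the recorded relatedness grade, and through it the two IRB routes that depend on relatedness.

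**Working it through.** The plan gives no figure to reproduce here. The check is whether each half of the prompt can discriminate under the dosing schedule.

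**Inputs.** From section 5.3: two packets a day, morning and afternoon, for 12 weeks, which is 12 × 7 = 84 days and 84 × 2 = 168 packets. Clock times and adherence are not given, so both are assumed below.

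**Onset half, full adherence.** The longer gap normally runs from an afternoon dose to the next morning's dose. An afternoon dose falls at or after noon and the next morning's before noon, so the gap is under 24 hours. With assumed times of 07:00/13:00, 08:00/14:00 and 09:00/17:00 the longest gaps are 18, 18 and 16 hours. Every on-treatment onset is therefore within 24 hours of a dose.

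**Onset half, missed packets, same times each day.** Two scheduled doses lie in any preceding 24 hours. One missed packet opens a gap of exactly 24 hours, so an onset is outside the window only if both were missed. If packets are missed independently with adherence *a*, and onsets are unrelated to the misses, the share inside is 1 − (1 − *a*)²:

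| Assumed adherence | Calculation | Share of onsets inside |
|---|---|---|
| 90% | 1 − 0.10² | 99% |
| 80% | 1 − 0.20² | 96% |
| 70% | 1 − 0.30² | 91% |

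Simulating 84 days under the three assumed schedules agreed to within about 0.1 percentage point.

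**Limits of those figures.** Illness or travel would cluster misses and lower the shares. Under fixed times, the chance that both packets were missed cannot exceed the overall miss rate 1 − *a*, so the floor is *a* itself: 90%, 80% or 70%. If times vary, one missed packet can be enough. Take doses at 08:00 and 13:00 on one day, with 10:00 and 17:00 planned for the next. If the 10:00 packet is missed, an onset at 14:00 that second day is 25 hours after the last dose.

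**Resolution half.** Four kinds of on-treatment event, set against the prompt as naturally read:

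| Event | Onset within 24 h | Resolved within 24 h | Prompt |
|---|---|---|---|
| Brief, caused by powder | yes | yes | met |
| Lasting, caused by powder | yes | no | not met |
| Brief, unrelated | yes | yes | met |
| Lasting, unrelated | yes | no | not met |

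The answer follows duration and not cause. A looser reading, in which resolution within 24 hours of *any* dose counts, does not rescue it. Nearly every resolution during dosing would then qualify, and the prompt would separate out only symptoms that do not clear while dosing continues, again counting them against relatedness.

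**Effect on the grade.** The documents give no event counts or durations, so the number of grades that would change cannot be calculated.

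**The case against.** The best reply is that the prompt decides nothing by itself. It is one item to consider, and clinical judgment sets temporality. The Investigator grades on all available information, and the grade definitions also point to other etiologies and to whether study procedures can be ruled out. The PI reviews and signs each form, and section 8.3 adds two geriatricians to help with relatedness. For a new lasting symptom, the first prompt points towards the product. Nor does the plan say which answer to the second prompt implicates the powder. All of this stands and limits the harm. It does not make the prompt a useful one: an item offered as evidence of temporal association is naturally read with *yes* as support, and if the direction is unclear, that is also a reason to reword.

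Four stronger readings are tempting, and the documents do not support them:

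- *That staff must grade relatedness from these two prompts alone.* The Investigator sentence and the grade definitions say otherwise. The event forms and the Manual of Procedures, which are not in the documents, may add more.
- *That a related event would escape the IRB.* Section 8.4 also provides for IRB reporting of any adverse event as appropriate after PI review, routine reporting of serious events, and logging and reporting of all others. None of these requires relatedness. The exposure is mainly one of route and timing. Expected gut effects would enter the relatedness-based route for non-serious events only if unexpected in nature, severity or frequency.
- *That a death, or "A persistent or significant disability/incapacity", could never be called related because it cannot resolve in a day.* The prompt concerns a symptom, whereas these are outcomes, and every serious event goes to the PI and co-investigators. Mechanical use of the prompt there is unlikely.
- *That the participant stopping rule is distorted.* Section 8.5 turns on whether a serious event is thought directly related, but does not cite this prompt.

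**Conclusion.** The point holds, and it is minor. As worded, the second prompt barely discriminates on onset. On resolution it leans against persistent product effects, including kinds of symptom the plan expects to track.

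For a fully adherent participant the onset half is met by every on-treatment event, without assuming particular clock times. The 99%, 96% and 91% figures for imperfect adherence rest on fixed dose times, independent misses and assumed adherence. The direction of the lean rests on the natural reading of the prompt.

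The consequence is confined to the recorded relatedness grade and the relatedness-based IRB routes. Events are logged whatever their grade, gut symptoms are asked about at each visit, counts by arm are unaffected, and no analysis in Chapter 6 uses the grade. The documents do not show that any safety decision would change.

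**What to change.** Replace the second consideration in section 8.4 with wording such as: *Whether the symptom began or worsened after the product was started, including any pattern relative to doses. Improvement after the product is held is supporting evidence where it can be assessed. Persistence does not count against relatedness.* Delete the condition of resolving within 24 hours.

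Onset after starting the powder will separate little by itself. The discrimination comes from the first consideration, the dose pattern and any response to holding the powder. The wording should not call for restarting the powder after a serious event.

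The cost is one reworded item, plus the adverse event forms if they repeat it. Possibly a few more events would be graded Possible and reported. Visits, sample size, analysis and section 8.5 are untouched.
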